5.4 Preparation and Administration of Study Treatment

Xenoport will supply Cleveland Clinic Fairview hospital and Cleveland Clinic Main Campus pharmacy with gabapentin enacarbil and identically looking placebo. Gabapentin enacarbil

or placebo will be administered orally with meals a day before the surgery, with sips of water pre-operatively and again with meals post-operatively. Both gabapentin enacarbil and placebo will have an identical package, with regards to appearance and physical properties. They will both be administered as oral tablets with sips of water or meals.

5.5 Subject Compliance Monitoring

Compliance with study drug will be monitored and recorded by study personnel based on information from the treating principal investigator and subjects. Subjects must be withdrawn from the study if they do not comply with the study drug regimen.

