4.4 Early Withdrawal of Subjects

Patients will be free to withdraw from study at any time. Subjects must be withdrawn from the study for the following reasons:

1. Voluntary withdrawal
2. Adverse event or serious adverse event deemed necessary by investigator for patient safety.
3. Unable to take medication for three post-operative days

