4.5 Data Collection and Follow Up for Withdrawn Subjects

1. Data obtained from electronic medical records will include: operation time, surgery type, intraoperative opioid consumption, postoperative opioid consumption in PACU and in ward, breakthrough pain medication requirements, pain scores in PACU and ward, requirement of antiemetics for nausea and vomiting, requirement of antihistaminic medications, requirement of laxatives for constipation, ambulation time, flatus, ileus, bowel movements, length of stay and any side effects or complications.
2. Preoperative and postoperative laboratory data including but not limited to renal function results will also be collected from electronic medical records. Patient functionality will also be recorded including, bathing, toileting, walking and moving.
3. Patients will be evaluated for pain (using numerical rating scale) (NRS) once in the PACU (Post-Anesthesia Care unit) every 15 minutes during the initial first hour after surgery and then on the first, second and third post-operative morning. Amount of opioids used, rescue anti-emetics used, nausea, vomiting and pain scores will be documented in EPIC.
4. With all study patients, post-operative pain at rest will be collected and reflected using the Numerical rating scale (NRS) pain scale. The patient is asked to rate the pain within (0-10), with zero indicating no pain and 10 indicating the worst imaginable pain.
5. Pain will be evaluated both at rest and after exercise as per physiotherapy protocol. This would be a global assessment of pain since the last assessment.
6. Patient satisfaction with their pain treatment will be questioned after 72 hours or at discharge whichever comes first using 0-5 scales and we will also use QoR-15 score to formally evaluate quality of recovery. The QoR-15 score is a validated scoring system allows quantification of patient's early postoperative health status, which is also a

description of quality of recovery. The QoR-15 score will be performed on 72 hours post op or at discharge whichever comes first.

7. Patients will be contacted by telephone at 3 months after surgery and queried regarding presence of new pain since surgery and its interference with activities of daily living. Phone call is made with the purpose of checking for pain conversion from acute to chronic and to check for any adverse event.

5. STUDY DRUG (or Device, Biologic, Treatment)

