5.7 Packaging

HORIZANT ER 600mg tablets will be overencapsulated by the CCF IDS pharmacy. A matching placebo capsule will be compounded by the pharmacy to match that of the active study drug. Both will be packaged in vials containing ten capsules each, and will be dispensed accordingly to RedCap randomization (10 tablets per bottle).

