6.2 Visit 1 (Day of Surgery)

Patients will be given GEn 600 mg single dose with sips of water 2 hours before surgery and then restarted within 6 hours of completion of surgery. GEn will be administered to the patient 600 mg bid for three post-operative days with meals.

Physical evaluations include monitoring vital signs, checking general well-being and pain evaluation both pre-operatively and post-operatively. Patients will be evaluated by orthopedic

surgeons pre-operatively and post-operatively as per their protocol. Physical therapy will evaluate the patients for pain, mobility and strength as per physical therapy protocol. Physical therapy and orthopedic surgeons will record and document their findings in EPIC.

Patients will be monitored throughout their stay in the hospital and will be asked to report any adverse event or any untoward event to the research fellow. Patients will be also be inquired for any side effects during the phone call made 3 months after surgery.

Patient discharged prior to 72 hours will be followed-up via phone call(s). Phone call followup will be performed once a day till 72 hours.

6.3 Visit 2 (Phone call).

Patients will be contacted by telephone at 3 months after surgery and queried regarding presence of new pain since surgery and its interference with activities of daily living. Phone call is made with the purpose of checking for pain conversion from acute to chronic and to check for any adverse event.

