7.2 Statistical Methods

The modified intention-to-treat approach will be utilized: patients who were randomized, had the procedure and received any amount of treatment will be included in the analysis. The per-protocol analysis (on patients who were randomized, had the procedure and followed the treatment regimen at least 50% of the times) will be conducted for the primary outcome as a sensitivity analysis.

First, randomized groups will be compared for balance on potentially confounding baseline demographic and preoperative variables using descriptive statistics.

Primary outcome. In the primary hypothesis, quality of postoperative analgesia will be characterized using both pain scores and total postoperative opioid consumption within 72 hours of the surgery or till discharge. We will consider gabapentin enacarbil group better than placebo group on the postoperative pain management if gabapentin enacarbil group is found noninferior (i.e., not worse) on both outcomes and superior on at least one of the outcomes. We define the a-priori noninferiority pain score delta as 1 point and the opioid delta as 1.1 for the ratio in geometric

means IV morphine equivalent doses (meaning 10% difference between group's median doses). Thus, our primary hypothesis will be assessed in a joint hypothesis-testing framework described by Mascha and Turan (42).

We will first estimate confidence intervals for the treatment effect for both pain score and opioid consumption. Assuming lognormal distribution of opioid consumption, we will evaluate the percent difference in geometric mean IV morphine equivalent dose between the two groups using a log-linear regression model. To evaluate the difference in mean pain scores we will first summarize the pain scores by computing time weighted average (TWA) pain score for each patient. Then we will use a linear regression model to assess the treatment effect on the TWA pain scores.

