8.5 Stopping Rules

Subjects must be withdrawn from the study if there is any adverse event or serious adverse event deemed necessary by investigator for patient safety.

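### Does withdrawing non-compliant patients from the study cost the modified ITT analysis their 72-hour outcomes, or contradict the 50% per-protocol rule?

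*Combined protocol and SAP*

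**What the plan says.** Three sections of the combined protocol and SAP take patients out of the study rather than off study drug.

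- Section 5.5: "Subjects must be withdrawn from the study if they do not comply with the study drug regimen". It defines no level of non-compliance.
- Section 4.4 lists three reasons: voluntary withdrawal, an adverse event where the investigator judges withdrawal necessary for safety, and "Unable to take medication for three post-operative days".
- Section 8.5: "Subjects must be withdrawn from the study if there is any adverse event or serious adverse event", a sentence that goes on to limit the rule to events where the investigator judges it necessary for safety.

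Other sections govern data and analysis.

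- Section 4.5 is headed "Data Collection and Follow Up for Withdrawn Subjects". It lists PACU and ward opioid use, pain scores in PACU and on three mornings, nausea, vomiting and antiemetics, satisfaction and QoR-15 at 72 hours or discharge, and the three-month call.
- Section 7.2 defines the modified ITT set: patients who were randomized, had the procedure and "received any amount of treatment will be included in the analysis". The per-protocol set, used only as a sensitivity analysis of the primary outcome, needs patients who "followed the treatment regimen at least 50% of the times".
- Section 6.2: "Patient discharged prior to 72 hours will be followed-up via phone call(s"), once a day until 72 hours.
- Section 5.7 fixes the dose count: "Both will be packaged in vials containing ten capsules each".

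**The concern.** Two things look wrong.

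First, 5.5 is mandatory and has no threshold, while 7.2 treats half adherence as enough for the per-protocol set. On a strict reading, a patient who takes 5 to 9 of the 10 doses is per-protocol in one section and must be withdrawn in another.

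Second, the modified ITT set needs outcomes to 72 hours or discharge from every treated patient. If a site took withdrawal to end data collection, the cumulative opioid total would be cut short or missing in exactly those patients whose stopping may depend on treatment and outcome. The bias could favour GEn if its side effects cause more stopping, or placebo if GEn reduces nausea and vomiting as hypothesised. No numbered item in 4.5 says that collection continues after withdrawal, and section 7 has no missing-data rule.

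**Working it through.** **The plan's own figure.** Inputs from 7.1 and 7.2: 50 per arm, CV 0.7, geometric mean ratio 0.63, one-sided 0.0125.

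- Log SD = sqrt(ln(1 + 0.7²)) = 0.631; SE = 0.631 × sqrt(2/50) = 0.126; effect = ln(0.63) = −0.462.
- A t-test with 98 df gives 91.5% power, which agrees with the stated figure of about 90%.

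**Section 5.5 against the 50% rule.** Doses (5.2, 5.7): 2 the day before + 1 before surgery + 1 after + 6 on POD 1–3 = 10. Half is 5, reached with the first POD 1 dose.

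- Section 5.5 governs conduct. The 50% rule defines an analysis set by doses taken.
- Withdrawal is not an exclusion criterion for either set in 7.2. A patient withdrawn after 6 of 10 doses has 60% adherence and belongs to both.
- So the two rules can hold together without non-compliance having to mean less than 50%.

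How often a strict reading of 5.5 would apply depends on a missed-dose rate that the documents do not give. Assuming independent misses, the share of patients missing at least one dose is 1 − (1 − p)^10: 9.6% at p = 1%, 18.3% at 2%, 40.1% at 5%, 65.1% at 10%. Fewer than 0.02% would take under half. Under that reading withdrawal could be common, so what matters is whether it stops data collection.

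**Does withdrawal stop data collection?** Section 4.5, under a heading about withdrawn subjects, names both components of the primary outcome and the data for the secondary ones. One of its items refers to all study patients. The natural reading is that withdrawn patients have the same data collected as everyone else. Inpatient opioid use and pain scores come from the electronic record, which runs on whatever the patient's study status.

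**Size if data were nevertheless lost.** The excess, the captured fraction and the 0.5 SD below are all assumptions.

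- Truncated totals: log shift = excess fraction × ln(captured fraction). For 5 of 50 in one arm with half captured, 0.10 × ln(0.5) = −0.069, so a true ratio of 1.00 reads 0.93 (excess on GEn) or 1.07 (excess on placebo). At 5% excess, 0.05 × ln(0.5) = −0.035: 0.97 or 1.04.
- Missing totals, with the lost patients' mean log dose 0.5 SD above their arm's mean: (0.10/0.90) × 0.5 × 0.631 = 0.035, so 0.97 or 1.04.
- Simulation of the opioid test alone (200,000 replicates, 5 of 50 totals halved in one arm): with no true effect, the claim rate moves from 1.2% to 3.9% (GEn) or 0.2% (placebo). At ratio 0.63, power moves from 91% to 97% or 78%.
- Equal loss in both arms (precision only): power 89.9% at 5% lost, 88.1% at 10%, 83.6% at 20%.
- Complete data to 72 hours or discharge: no shift.

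**The case for a change.** The best case for a change is that a heading is not an instruction. The items in 4.5 read like the ordinary schedule, and none separates stopping drug from withdrawing consent. Where the authors wanted follow-up to continue, as after early discharge in 6.2, they wrote a sentence for it. Being in the analysis set does not create data. The electronic record cannot supply QoR-15 or the three-month call, which need contact with the patient. The 3.9% claim rate above would not be trivial, and clarifying wording would cost little.

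Part of this stands: the wording in 4.5 is generic, 5.5 has no threshold, and section 7 does not say how missing outcomes are handled. The rest is weaker. The sentence in 6.2 promises calls but names no outcome, whereas 4.5 names them. The clause on inability to take medication in 4.4 can be read as known only near the end of the 72-hour window, when little of the opioid total is left to lose. The 3.9% is for the opioid test alone; a positive trial by that route also needs noninferiority on pain. It also needs a between-arm excess and a half-captured total, for which the documents give no basis.

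**Conclusion.** No change is needed. Followed as written, the plan collects withdrawn patients' primary and secondary outcomes (4.5) and analyses every treated patient who had the procedure (7.2). The compliance rule in 5.5 and the 50% sensitivity-set definition can both apply to the same patient, so the analysis sets do not contradict each other.

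What remains is missing detail: an explicit statement that collection continues after drug is stopped, and a rule for outcomes still missing. An analyst applying 7.2 would keep these patients in the modified ITT set and use their recorded data. The shifts to 0.93 or 1.07 show what selective loss could do, not what the plan produces. They rest wholly on the assumed 10% excess and half capture, and are zero if data are complete. The conclusion assumes that sites read 4.5 as its heading indicates. Data lost because a patient withdraws consent fall outside it.

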5.6 Prior and Concomitant Therapy

Patient will not receive any gabapentinoids from the start of study drug to the end of postoperative 72 hours period. All other pain medications will be allowed.

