1. INTRODUCTION

1.1 Background

Pain control

Hip and knee replacements are the most common elective surgeries in the U.S.A. Pain control after surgery remains challenging despite advances in surgical techniques and new treatment modalities (32-33). Three-quarters of surgical patients in the United States experience postoperative pain and are unsatisfied with their analgesia (28-29). The major cause of pre-operative anxiety in any surgical patient is fear of postoperative pain (18). Pain is a psychological sensory experience, which is caused by various factors. Surgery results in tissue damage which leads to postoperative pain. Studies in recently developed animal models of postoperative pain have advanced our knowledge of the mechanisms of pain resulting from surgical incision and associated tissue injury.

Post-operative pain has numerous etiologies and many contributing factors; it thus usually responds best to multimodal approaches (28-29). Pain may result from tissue trauma secondary to stretching and compression or direct nerve injury as a result of surgical incisions and burns (1-6). Pain is aggravated by coughing, sneezing, moving etc. or any other movement, which increases pressure over the surgical area. Most clinicians consider nerve blocks to be the optimal approach, but many patients nonetheless require opioids.

Ineffective pain control results in increased mortality and morbidity (7-8, 22). For example, surgery provokes immune depression, which may have deleterious effects. Reducing postoperative pain may speed mobilization and reduce pulmonary and cardiac complications, whereas early mobilization reduces the risk of deep vein thrombosis. This implies that, if post-operative pain is treated effectively, then costs of care could be decreased significantly.

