3.2 Primary Study Endpoints

To assess whether gabapentin enacarbil improves quality of postoperative analgesia characterized by decreased pain and/or opioid requirements after hip or knee surgery. Cumulative opioid consumption in the PACU and floor for the first 72 hours after surgery or till discharge whichever comes first. The total dose of opioid administered includes the background analgesia provided by morphine PCA, fentanyl PCA or hydromorphone PCA, rescue doses of IV fentanyl, IV

hydromorphone, and PO oxycodone. All opioids will be converted into morphine equivalents to standardize opioid consumption (10 mg of IV morphine = 100 mcg of IV fentanyl = 1.5 mg of IV hydromorphone = 20 mg of PO oxycodone) the total number of requested PCA boluses will also be recorded, along with the number of requests that were actually delivered.

Postoperative pain intensity will be evaluated in the PACU using a 0-10 Numeric Rating Scale (NRS), where 0 is no pain and 10 is the worst possible pain. Pain will be assessed every 15 min for the first one hour after surgery and then every morning for three post-operative days as long as the patients are hospitalized.

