4. SUBJECT SELECTION AND WITHDRAWAL

4.1 Inclusion Criteria

To be eligible for entry into this study, candidates must meet all of the following eligibility criteria at the time of randomization:

1. Men or women 18-85 years of age.
2. Scheduled for elective knee or hip arthroplasty with spinal anesthesia.

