4. Data obtained from electronic medical records will include: operation time, surgery type, intraoperative opioid consumption, postoperative opioid consumption in PACU and in ward, breakthrough pain medication requirements, pain scores in PACU and ward, requirement of antiemetics for nausea and vomiting, requirement of antihistaminic medications, requirement of laxatives for constipation, ambulation time, flatus, ileus, bowel movements, length of stay and any side effects or complications. Preoperative and postoperative laboratory data including but not limited to renal function will also be collected from electronic medical records. Patient functionality will also be recorded including, bathing, toileting, walking and

moving.

⁸ Phone calls will be made purely to remind patients to take their pre-operative medication.

⁹ Phone calls will be made to check for any adverse event and with the intention to assess chronic pain.

¹⁰ Phone call made for follow-up if the patient is discharge prior to 72 hours.

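### Nerve blocks, infiltration and opioid in the spinal are left free, but no listed data item captures them and neither primary regression names a covariate: a modest loss of precision and reporting, not a bias

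*Combined protocol and SAP*

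**What the plan says.** - **Concomitant analgesia.** Section 5.6 bars gabapentinoids from the start of study drug to 72 hours after surgery and then states: "All other pain medications will be allowed".
- **Anesthetic.** Section 4.1 admits patients "Scheduled for elective knee or hip arthroplasty with spinal anesthesia". The content of the spinal is not described.
- **Nerve blocks.** Their one mention is in section 1.1: "Most clinicians consider nerve blocks to be the optimal approach, but many patients nonetheless require opioids".
- **Data collected.** Sections 4.5 and 6.4 (footnote 7) list "intraoperative opioid consumption, postoperative opioid consumption in PACU and in ward", together with breakthrough medication, laxatives, Apfel score and much else. A block, an infiltration or the spinal's content is not listed.
- **Opioid endpoint.** Section 3.2 counts "Cumulative opioid consumption in the PACU and floor for the first 72 hours after surgery or till discharge whichever comes first". Opioid given in theatre is outside it.
- **Analysis.** Section 7.2 compares "geometric mean IV morphine equivalent dose between the two groups using a log-linear regression model" and, for pain, says "we will use a linear regression model to assess the treatment effect on the TWA pain scores". No covariate is named in either model. Baseline balance is described only for demographic and preoperative variables. Randomisation is stratified by hip versus knee alone (section 5.3).

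**The concern.** A block, an infiltration or opioid in the spinal could plausibly alter both pain and opioid need during the 72-hour window. If their use varies between patients, that variation goes into the residual of both primary models. Opioid in the spinal could at most appear within the intraoperative total, which no planned analysis uses.

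Two things are at stake. The first is precision in a trial fixed at 100 patients, whose opioid noninferiority margin is narrow (ratio 1.1) and where failing noninferiority on either outcome stops superiority testing. The second is interpretation: a reader of the results could not tell from the planned tables whether the arms differed in regional technique.

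**Working it through.** **Inputs from the plan (sections 7.1 and 7.2).** 50 per arm; coefficient of variation 0.7; target ratio 0.63; one-sided superiority level 0.0125; noninferiority at one-sided 0.025 with opioid margin 1.1.

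**Plan's own figure.**
- Log variance = ln(1 + 0.7²) = ln 1.49 = 0.3988, so log SD = 0.6315.
- SE of the log ratio = 0.6315 × √(2/50) = 0.1263.
- Effect = |ln 0.63| = 0.4620.
- Power by noncentral t with 98 df, one-sided 0.0125, is 91.5%. The stated power of about 90% is reproduced.

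**Assumptions, not in the documents.** A share p = 0.3 to 0.5 of patients is exposed to a technique that lowers 72-hour opioid use by d = 20% to 40%. The plan gives no frequency or effect for blocks or spinal opioid, and no variability for pain scores, so only the opioid outcome can be sized.

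**Share of log variance explained** = p(1−p) × [ln(1−d)]² / 0.3988.
- Low end (p = 0.3, d = 0.2): 0.21 × 0.2231² / 0.3988 = 0.026.
- High end (p = 0.5, d = 0.4): 0.25 × 0.5108² / 0.3988 = 0.164.

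**Power after adjustment**, with adjusted SE = 0.1263 × √(1 − share explained):

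| Case | Share explained | SE | Superiority power at 0.63 | Noninferiority power at true ratio 1 |
|---|---|---|---|---|
| Unadjusted | 0 | 0.1263 | 91.5% | 11.3% |
| Low end, covariate perfectly measured | 0.026 | 0.1246 | 92.2% | 11.5% |
| High end, covariate perfectly measured | 0.164 | 0.1155 | 95.6% | 12.7% |
| Low end, planned and given correlate 0.6 | 0.026 × 0.36 = 0.009 | 0.1257 | 91.7% | 11.3% |
| High end, planned and given correlate 0.6 | 0.164 × 0.36 = 0.059 | 0.1225 | 93.1% | 11.7% |

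The correlation of 0.6 is an illustration. As p approaches 0 or 1, p(1−p) goes to zero and the gain disappears.

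**Imbalance against the margin.** The SD of the between-arm difference in exposure is √(2p(1−p)/50) = 0.092 to 0.100. A one-SD imbalance moves the opioid ratio by exp(0.092 × 0.2231) − 1 = 2.1% to exp(0.100 × 0.5108) − 1 = 5.2%. On the log scale that is 21% to 54% of ln 1.1 = 0.0953.

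**Is that on top of the interval?** No. In simulation (200,000 trials per scenario) with the factor left out of the model, type I error stayed nominal. For noninferiority it was 0.0255 (p = 0.5, opioid use multiplied by 0.6) and 0.0247 (p = 0.3, multiplied by 0.5), against 0.025. For superiority it was 0.0128 in both scenarios, against 0.0125.

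**The case against.** The strongest objection is that, with concealed and blinded randomisation, chance imbalance in technique is ordinary random error. It acts in either direction and is already part of the outcome SD, hence of the interval that decides noninferiority. This stands. A reader who sets the 21-54% figure beside the margin might infer that an unrecorded imbalance could itself use up the opioid margin, or make the result biased. The documents do not support that: the shift is not additional to the interval, and error rates are preserved.

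Three further objections have force.

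- The documents do not say how often blocks are used here, whether use varies between patients, or that any opioid goes into the spinal. Section 1.1 offers one general sentence about blocks. A strong effect on both co-primaries is an assumption.
- A reader might say technique is recorded nowhere. The case report form is not among the documents, and data are drawn from the electronic record, so later retrieval may be possible. The supportable statement is that no listed data item names it.
- The power gain computed for technique actually given is an upper bound for a covariate based on the plan.

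What remains is the omission itself. A valid interval on average over randomisations does not tell a reader of one trial whether its arms differed, and retrieval after the fact is not a prespecified covariate.

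**Conclusion.** The point holds as a low-priority improvement in precision and reporting. The plan leaves analgesic technique free, lists no field for it and prespecifies no adjustment. There is no bias and no type I inflation.

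Under the assumed ranges, opioid-superiority power would rise by about 1 to 4 percentage points at best, and by about 2 points or less if plan and practice correlate only 0.6. The noninferiority step is hardly helped at a true ratio of 1. There the obstacle is a margin of 0.0953 against an SE of 0.1263, a separate matter that covariate adjustment does not solve. The effect on the pain co-primary cannot be sized from the documents.

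**What to change.** 1. Add fields, completed from the anesthesia record, for any nerve block or infiltration given (with type) and any opioid given in the spinal. Tabulate both by arm.
2. Where the planned technique is known at the pre-operative visit, record it before randomisation: planned block or infiltration (yes/no) and planned spinal opioid (yes/no).
3. State in section 7.2 that both primary regressions include the planned technique and the hip/knee stratum as covariates.
4. State that the technique actually given is reported and not used as a covariate. The study calendar places randomisation at the pre-operative visit, so what is given later, including any block in response to pain, is a post-randomisation event.

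The cost is two fields for the technique given, two yes/no entries for the plan, and a short addition to section 7.2. Adjustment uses two degrees of freedom for planned technique and one for hip/knee, out of 98. Planned and given technique will sometimes differ, which reduces the gain. No patient's care changes.
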